**Table 1-1: Schedule of activities**

Assessments	Screening Period	In-Clinic Period										Ambulatory Period									
		Admission	Dosing																	SFU/WD	
			Weeks	-4 to -1	0	1										1	2	2	3		3
Days	-28 to -2	-1 a	1				2	3	4	5 b	7	10	13	16	19	22	29	43	57		
Hours			0	4	6	8	12	24	48	72	96										
Informed consent	X																				
Inclusion/exclusion criteria	X	X																			
Randomization c			X																		
IMP administration d			■																		
Demography	X																				
Prior and concomitant medications	X	X	X	X	X	X	X	X	X	X	X	X	X	X	X	X	X	X	X		
SARS-CoV-2 testing (PCR)	X	X									X								X		
Influenza, tetanus, and SARS-CoV-2 antibody assessment	X	X									X								X		
Study participant card e			X																		
Medical/procedure history	X																				
Physical examination f	X	X									X								X		
Pregnancy test g	X	X															X		X		
Serum FSH level h	X																				
Tuberculosis test and questionnaire	X																				
Alcohol urine test and urine drug screen	X	X																			

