**Table 1-1: Schedule of activities**

Assessments	Screening Period	In-Clinic Period										Ambulatory Period									
		Admission	Dosing																	SFU/WD	
Weeks	-4 to -1	0	1										1	2	2	3	3	4	5	7	8
Days	-28 to -2	-1 a	1					2	3	4	5 b	7	10	13	16	19	22	29	43	57	
Hours			0	4	6	8	12	24	48	72	96										
Anti-rozanolixizumab antibodies u			X										X		X		X		X		
Headache questionnaire f			X	X	X	X	X	X	X	X	X	X									
Neurological assessment s			X	X	X	X	X	X	X	X	X										
Serum complement (C3, C4), and cytokines and plasma complement (C3a, C5a) t			X																		

AE=adverse event; CSF=cerebrospinal fluid; CT=computed tomography; ECG=electrocardiogram; FSH=follicle-stimulating hormone; IgG=immunoglobulin G; IMP=investigational medicinal product; ISRQ=injection site reaction questionnaire; MP>manual push; PCR=polymerase chain reaction; PK=pharmacokinetic(s); SARS-CoV-2=severe acute respiratory syndrome coronavirus 2; SC=subcutaneous(ly); SFU=Safety Follow-Up; SIAQ=self-injection assessment questionnaire; VAS=visual analog scale; WD=withdrawal

a Participants may be admitted into the clinic in the evening of Day -2 for the In-Clinic Period.

b Participants discharged during Day 5 at the discretion of principal investigator.

c Randomization should be performed on Day 1 before dosing and after all predose assessments and procedures have been completed.

d Rozanolixizumab will be administered as an SC infusion by syringe driver at a [REDACTED] or by MP through self-administration at a [REDACTED]

e This card is an emergency contact card and will be given to the participant when he/she is randomized in the clinical study (Day 1).

f A full physical examination will be performed at the Screening Visit, Day -1, and SFU. A brief symptom-led physical examination should be performed on Day 5.

g Serum pregnancy tests will be performed at the Screening Visit and on Day -1 and 29 and at the SFU Visit for all women with childbearing potential.

h Only for postmenopausal women (for at least 1 year post-menopause before the Screening Visit) not using hormonal contraception or hormonal replacement therapy.

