In UP0060, [REDACTED]-dose SC administration of rozanolixizumab to healthy Japanese, Chinese, and Caucasian study participants was generally well tolerated with an acceptable safety profile after [REDACTED] SC administration of [REDACTED] doses. Overall, patterns in the incidence of TEAEs observed in Japanese and Chinese study participants were generally comparable to those observed in Caucasian participants. In all study participants, a numerically higher incidence of TEAEs was reported for study participants receiving rozanolixizumab (38 participants [77.6%] reported 115 TEAEs) compared with placebo (10 participants [62.5%] reported 23 TEAEs). Among participants receiving rozanolixizumab, there was a trend towards increased incidence of TEAEs with higher doses (55.6%, 75.0%, and 90.0% of participants in the rozanolixizumab [REDACTED] dose groups, respectively). Three participants (6.1%) reported 4 TEAEs of special monitoring (diarrhea [2 events], abdominal pain [1 event], and vomiting [1 event]) in the [REDACTED] cohort, all of moderate intensity. The [REDACTED] dose was concluded by the investigator to be not well tolerated by 1 Caucasian volunteer who reported moderate headache. Dose-dependent reductions in IgG and IgG subclasses, similar to that observed in UP0018, were seen following administration of rozanolixizumab in all 3 ethnicities. Tetanus- and influenza A virus-specific IgG concentrations over time were similar to total IgG following the administration of rozanolixizumab, generally reaching the lowest levels around Day 10 and returning close to Baseline by Day 57; the geometric mean concentrations for tetanus- and influenza A virus-specific antibodies generally remained at acceptable levels for

protection time in all ethnic and dose groups. Overall, the mean value of albumin remained within the normal range over time, and no clinically relevant changes from Baseline were observed. All injection site reactions observed for rozanolixizumab were self-limiting, short-term, and of mild intensity.

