**Table 3-1: Study objectives and endpoints**

Objectives	Endpoints/Estimands

 
To evaluate the effects of rozanolixizumab on the concentrations of IgG on tetanus, influenza A virus-specific IgG antibody, and COVID-19 vaccinated/previously infected participants
 
	
 
Values and change from Baseline in serum IgG concentrations at each scheduled assessment during the In-Clinic and SFU Periods
 
Values and change from Baseline in tetanus, influenza A virus-specific IgG antibodies, and COVID-19 vaccinated/previously infected participants during the In-Clinic and SFU Periods
 

 
To assess total volume, total time, and infusion rate for MP and syringe driver
 
	
 
Volume of IMP administration
 
Time from start to completion and resultant infusion rate of IMP administration
 
Time of infusion setup for both modes of administration
 

 
To assess acceptability of SC rozanolixizumab administration by MP vs syringe driver
 
	
 
Postdose infusion site pain visual analog scale with IMP administration
 

 
To assess the experience with SC infusions
 
	
 
Pre- and postdose SIAQ for MP administration
 
Postdose ISRQ for syringe driver administration
 

Other Safety	

 
To evaluate changes from Baseline in vital signs, 12-lead electrocardiogram, and laboratory measurements following [REDACTED] doses of rozanolixizumab administered by SC MP vs syringe driver in healthy study participants
 
	
 
Vital signs measurements (blood pressure, pulse rate, respiratory rate, and body temperature), 12-lead electrocardiogram, and local tolerability assessments at each scheduled assessment during the In-Clinic and SFU Periods
 
Changes from Baseline in clinical laboratory assessments will consist of hematology including coagulation, clinical chemistry, and urinalysis at each scheduled assessment during the In-Clinic and SFU Periods
 

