5.5.2 Exploratory Analyses on the effect of rozanolixizumab on infection specific IgG

Observed values at baseline and at SFU and change from Baseline to SFU in IgG concentrations will be summarized descriptively for each treatment group for the following virus specific IgG concentrations

Tetanus specific IgG

Influenza A virus-specific IgG antibodies,

SARS Cov-2 antibodies for COVID-19 vaccinated and/or previously infected participants

For SARS-COV-2 antibodies, the summary table will present one row for vaccinated participants, a second row for previously infected participants, and a final row for those with both (if any). In addition to the summary table, the data for the above specific antibodies will be listed for all the collected timepoints.

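### Infection-specific IgG is sampled after dosing only on Day 5 and Day 57, which misses the fall expected to be deepest near Day 10, and the SAP tabulates only Day 57, where little change is expected

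*Protocol*

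**What the plan says.** The exploratory objective in Protocol Table 3-1 reads: "To evaluate the effects of rozanolixizumab on the concentrations of IgG on tetanus, influenza A virus-specific IgG antibody, and COVID-19 vaccinated/previously infected participants". Its endpoint is "Values and change from Baseline in tetanus, influenza A virus-specific IgG antibodies, and COVID-19 vaccinated/previously infected participants during the In-Clinic and SFU Periods".

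Table 1-1 has one row for these samples, "Influenza, tetanus, and SARS-CoV-2 antibody assessment", with four marks: Screening, Day -1, Day 5 and the SFU visit on Day 57.

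Protocol Section 2.2 gives the expected time course from UP0060: "Tetanus- and influenza A virus-specific IgG concentrations over time were similar to total IgG following the administration of rozanolixizumab", with levels "generally reaching the lowest levels around Day 10 and returning close to Baseline by Day 57".

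SAP Section 5.5.2 states the analysis: "Observed values at baseline and at SFU and change from Baseline to SFU in IgG concentrations will be summarized descriptively for each treatment group". Results at other time points are listed but not summarised.

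**The concern.** The protocol expects the antibodies to be lowest around Day 10, yet nothing is measured between Day 5 and Day 57. Section 2.3 already accepts that the drug will lower vaccine-specific IgG. The informative questions are how far levels fall and for how long, and the planned samples answer neither directly.

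The SAP then reports the less informative of the two post-dose samples. A table of change from Baseline to Day 57 describes recovery. A reader who sees only that table could take a near-zero change to mean that the drug had little effect on these antibodies.

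**Working it through.** The documents give no power, precision or effect-size figure for this endpoint, so there is no plan figure to reproduce.

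**1. Confirm the sampling days.** The marks in the antibody row stand in the same positions as those in the physical-examination row. Footnote f to that row names Screening, Day -1 and SFU, and adds: "A brief symptom-led physical examination should be performed on Day 5". The third antibody mark is therefore Day 5 (96 hours).

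**2. Compare with total IgG.** The gap between the two post-dose antibody samples is 57 − 5 = 52 days. Total IgG is sampled at 24, 48, 72 and 96 hours and on Days 7, 10, 13, 16, 19, 22, 29, 43 and 57, which makes 13 post-dose points. Eight of them (Days 7 to 43) lie inside that gap.

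**3. Share of the maximum fall visible on Day 5.** Dosing is on Day 1, so Day 5 is 4 days after dosing and Day 10 is 9 days after. The shape of the decline is not given and is assumed here. L is a lag in days before the fall begins, and k is a rate per day.

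- Straight line: share = (4 − L)/(9 − L).
- First-order: share = [1 − exp(−k(4 − L))]/[1 − exp(−k(9 − L))].

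| Lag L | Straight line | k = 0.05 | k = 0.1 | k = 0.2 | k = 0.3 |
|---|---|---|---|---|---|
| 0 | 4/9 = 44% | 50% | 56% | 66% | 75% |
| 1 | 3/8 = 38% | 42% | 47% | 57% | 65% |
| 2 | 2/7 = 29% | 32% | 36% | 44% | 51% |

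The range is 29% to 75%. By the protocol's own description, the share left on Day 57 is close to zero.

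**4. Could Day 5 show an effect at all?** Assume a maximum fall of 30% to 50%. The Day 5 mean change then runs from −30 × 2/7 = −8.6% to −50 × 0.75 = −37.5%. The 95% CI half-width for a mean is t(0.975, n − 1) × SD/√n. With an assumed SD of 10 to 20 percentage points:

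| Active participants | Half-width (points) |
|---|---|
| 24 (all) | 4.2 to 8.4 |
| 12 (one method) | 6.4 to 12.7 |
| 6 (one cohort) | 10.5 to 21.0 |

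Pooled over 24, a fall is distinguishable from zero throughout, but only just in the worst combination (8.6 against 8.4). In a single cohort it may not be.

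**5. Duration.** On an assumed straight-line recovery from Day 10 to Day 57, the share of the maximum fall remaining is (57 − 29)/47 = 60% on Day 29 and (57 − 43)/47 = 30% on Day 43. Neither day is sampled for these antibodies.

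**6. SAP against endpoint.** The endpoint covers both the In-Clinic and SFU Periods. Day 5 closes the first and Day 57 closes the second. The SAP summary uses only Day 57, so the In-Clinic part of the endpoint appears only in a listing.

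**The case against.** The case for the plan is a fair one.

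- The objective asks for effects, and neither it nor the endpoint names a lowest level. Maximum decrease and time to minimum are endpoints for total IgG only. One sample in each named period meets the endpoint as worded.
- Total IgG is followed closely through Day 10, and Section 2.2 says that tetanus and influenza A antibodies ran in parallel with it.
- Section 2.2 also reports that those antibodies generally stayed at acceptable levels in UP0060, and the present plan sets no protective threshold to test.
- The endpoint is exploratory, in a preliminary study with no formal sample size.

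These points limit the concern without removing it. Total IgG is an indirect substitute: it gives no antigen-specific concentration, and the reported parallel covers only tetanus and influenza A. UP0060 dosed by body weight. Section 4.2 says that the dose it discusses had not been given to healthy participants under 50 kg, so the depth of fall seen there need not carry over. None of the four points defends a summary table that leaves out Day 5.

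A reader might infer something stronger, namely that the schedule cannot show any effect on these antibodies. The documents do not support that. Day 5 lies on the declining limb and should show a partial fall. The risk that the result reads as no effect comes mainly from the SAP's choice of time point, and tabulating Day 5 would largely remove it.

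**Conclusion.** The point holds in limited form. The schedule misses the expected maximum reduction in infection-specific IgG and its duration, so the data would understate the effect: Day 5 shows about 29% to 75% of the maximum under the assumed shapes, and Day 57 close to none. The SAP compounds this by summarising only Day 57.

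The sampling days and the timing of the low point come from the protocol. The decline shapes, the depth of fall and the SDs are assumptions, because the documents do not show those figures. The Day 10 evidence concerns tetanus and influenza A only, so extending it to SARS-CoV-2 antibodies is an inference. The SAP also summarises the latter only for vaccinated or previously infected participants. Of the 32 participants, 24 receive active drug, and they carry the information on the size of the fall. The primary safety endpoint is unaffected.

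**What to change.** 1. In SAP Section 5.5.2, summarise value and change from Baseline at every collected post-dose time point, including Day 5, and label Day 57 as a measure of recovery. This needs no new data.
2. In Protocol Table 1-1, add the antibody assessment to the Day 10 visit and summarise it in the same table. Blood is already drawn at that visit for total IgG, PK, hematology, chemistry and anti-drug antibodies. The cost is about 32 more assays per antibody (at most 3 × 32 = 96 in all) and a small extra blood volume within the 500 mL limit. No new visit is needed. Protocol Section 8 already provides for added time points, and Amendment 2 added two for clinical chemistry.
3. If Day 10 cannot be added, state in the SAP and the report that the maximum reduction in infection-specific IgG is not estimable from this study. Stored material should not be counted on. The storage provisions in Protocol Sections 8.9 and 8.9.1 concern biomarker backup samples and anti-drug antibody samples, and do not clearly provide a Day 10 sample for these assays.

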### 2.3 Benefit/risk assessment

The healthy study participants included in this study will receive no medical benefit from participation. The risks from taking part in the study will be minimized through the selection of appropriate dose levels, selection of appropriate study participants defined by the inclusion/exclusion criteria, and safety monitoring. In UP0106, safety and tolerability of rozanolixizumab will be monitored through the use of sentinel pair dosing (Section 4.1 and Section 4.2), and predefined stopping rules will apply to all cohorts (see Section 6.7). Safety will be reviewed by a Safety Monitoring Committee (SMC) (Section 9.7). In addition, the Rapid Alert process will be in place throughout the study to ensure that exposure to the study medication is stopped if a reported event meets the stopping criteria (see Appendix 8 [Section 10.8]).

To date, human clinical data available for rozanolixizumab are derived from completed Phase 1 studies (UP0018 and UP0060) in healthy study participants and completed Phase 2 studies in study participants with primary ITP (TP0001) and generalized MG (MG0002). Based on other observations from the current nonclinical and clinical studies with rozanolixizumab and clinical studies with other IgG antibodies in humans, the potential adverse effects that may be anticipated include gastrointestinal disturbances, headaches, infusion and hypersensitivity reactions, local tolerability and injection site reactions, and effects on vaccination response.

Clinical development for rozanolixizumab is proceeding with dosing via the SC route of administration only. The Reference Safety Information provided in the current IB is therefore based on the safety experience with SC dosing and is the Reference Safety Information for all ongoing and planned clinical studies with rozanolixizumab. It will be used to perform the event expectedness assessments for expedited reporting and annual safety reporting.

Vaccinations, including coronavirus disease-19 (COVID-19) vaccination, are not allowed during the study (Section 6.5.2). Restrictions on use of live vaccines have been identified in the exclusion criterion #29. If vaccination with non-live vaccines (including current available COVID-19 vaccines) is considered necessary, the degree of protection afforded by vaccination under treatment may be compromised during and after treatment with rozanolixizumab.

Based on its mechanism of action, rozanolixizumab will reduce total IgG levels including vaccine-specific IgG. However, it is unlikely that the immune response to the vaccine will be compromised by FcRn inhibition, particularly after administration of a [REDACTED] dose of rozanolixizumab.

In order to keep potential confounding of safety variables to a minimum and to allow differentiation of safety profiles of the IMP and COVID-19 vaccine, the Screening Visit should not be scheduled before at least 2 weeks after the COVID-19 vaccination (Section 8.2.12).

More detailed information about the known and expected benefits and risks and reasonably expected adverse events (AEs) of rozanolixizumab may be found in the IB. The current IB

reflects the safety profile of SC rozanolixizumab as it is known and may change with the accumulation of additional data.

### 3 OBJECTIVES AND ENDPOINTS

The objectives and corresponding endpoints for this study are presented in [Table 3-1](#).

**Table 3-1: Study objectives and endpoints**

Objectives	Endpoints/Estimands
Primary	

 
To evaluate the safety and tolerability of a [REDACTED] SC dose of rozanolixizumab administered to healthy participants by MP vs syringe driver
 
	
 
Incidence of TEAEs
 

Secondary	

 
To assess the PK and PD of a [REDACTED] SC dose of rozanolixizumab administered by MP vs syringe driver
 
	PK endpoints: 
 
<math>C_{max}</math>, <math>t_{max}</math>, <math>AUC_{(0-t)}</math>
 
 PD endpoints: 
 
Baseline-corrected area under the Total IgG-time curve
 
<math>R_{min}</math>
 
<math>t_{min}</math>
 

Exploratory	

 
To compare the PK and PD of a [REDACTED] SC dose of rozanolixizumab administered by MP vs syringe driver
 
	
 
PK comparisons: <math>C_{max}</math>, <math>AUC_{(0-t)}</math>
 
PD comparison: Baseline-corrected Total IgG AUC
 

 
To evaluate the immunogenicity of rozanolixizumab following SC administration
 
	
 
Anti-rozanolixizumab antibody screening status (positive or negative screen), confirmatory status (positive or negative immunodepletion), and the titer for “positive immunodepletion” samples at each scheduled assessment during the In-Clinic and SFU Periods
 

**Table 3-1: Study objectives and endpoints**

Objectives	Endpoints/Estimands

 
To evaluate the effects of rozanolixizumab on the concentrations of IgG on tetanus, influenza A virus-specific IgG antibody, and COVID-19 vaccinated/previously infected participants
 
	
 
Values and change from Baseline in serum IgG concentrations at each scheduled assessment during the In-Clinic and SFU Periods
 
Values and change from Baseline in tetanus, influenza A virus-specific IgG antibodies, and COVID-19 vaccinated/previously infected participants during the In-Clinic and SFU Periods
 

 
To assess total volume, total time, and infusion rate for MP and syringe driver
 
	
 
Volume of IMP administration
 
Time from start to completion and resultant infusion rate of IMP administration
 
Time of infusion setup for both modes of administration
 

 
To assess acceptability of SC rozanolixizumab administration by MP vs syringe driver
 
	
 
Postdose infusion site pain visual analog scale with IMP administration
 

 
To assess the experience with SC infusions
 
	
 
Pre- and postdose SIAQ for MP administration
 
Postdose ISRQ for syringe driver administration
 

Other Safety	

 
To evaluate changes from Baseline in vital signs, 12-lead electrocardiogram, and laboratory measurements following [REDACTED] doses of rozanolixizumab administered by SC MP vs syringe driver in healthy study participants
 
	
 
Vital signs measurements (blood pressure, pulse rate, respiratory rate, and body temperature), 12-lead electrocardiogram, and local tolerability assessments at each scheduled assessment during the In-Clinic and SFU Periods
 
Changes from Baseline in clinical laboratory assessments will consist of hematology including coagulation, clinical chemistry, and urinalysis at each scheduled assessment during the In-Clinic and SFU Periods
 

**Table 3-1: Study objectives and endpoints**

Objectives	Endpoints/Estimands

 
To further evaluate the safety and tolerability of a █████ SC dose of rozanolixizumab administered to healthy participants by MP vs syringe driver
 
	
 
Occurrence of serious TEAEs
 
Occurrence of treatment-related TEAEs
 
Occurrence of TEAEs leading to withdrawal
 
Occurrence of AEs of special monitoring
 
Comparison of TEAEs for MP vs syringe driver
 
Serum complement (C3, C4), and cytokines and plasma complement (C3a, C5a)
 

AE=adverse event; AUC=area under the concentration-time curve;  $AUC_{(0-t)}$ =area under the concentration-time curve from 0 to time t;  $C_{max}$ =maximum plasma concentration; COVID-19=coronavirus disease-19; IgG=immunoglobulin G; IMP=investigational medicinal product; MP=manual push; ISRQ=injection site reaction questionnaire; PD=pharmacodynamic(s); PK=pharmacokinetic(s);  $R_{min}$ =maximum decrease in total plasma IgG; SC=subcutaneous(ly); SFU=Safety Follow-Up; SIAQ=self-injection assessment questionnaire; TEAE=treatment-emergent adverse event;  $t_{max}$ =time to maximum plasma concentration;  $t_{min}$ =time to minimum IgG level

This document cannot be used to support any applications for marketing authorization or extensions of the current application and any extensions of the current application

## 4 STUDY DESIGN

### 4.1 Overall design

This Phase 1 study is a randomized, participant-blind, investigator-blind, placebo-controlled safety/tolerability, PK, and PD evaluation of a [REDACTED] rozanolixizumab SC dose administered to healthy participants by either a programmed syringe driver or by MP via self-administration. As rozanolixizumab has not been administered SC to humans by MP, this study represents a preliminary assessment of the MP method prior to recommendation of this administration technique in the clinical dosing of rozanolixizumab.

Participants will be divided into 2 body weight categories:  $\geq 35$  to  $< 50$ kg and  $\geq 50$ kg. Within the higher body weight category, 16 participants will be randomly allocated to syringe driver or MP cohorts and, subsequently, to rozanolixizumab (6 participants total) or placebo (2 participants total) (Figure 1-1). Participants of lighter body weights between  $\geq 35$  to  $< 50$ kg are being investigated to a) support the newly recommended rozanolixizumab dosing with a fixed dose of [REDACTED] in adults of  $\geq 35$ kg to 50kg (via syringe driver administration) and (b) to assess the MP method for a [REDACTED] IMP volume.

Within the lower body weight category, the allocation to either syringe driver or MP will be determined by order of recruitment rather than randomization. The first 8 participants will be allocated to the syringe driver cohort and randomly allocated to receive either rozanolixizumab [REDACTED] (6 participants total) or placebo (2 participants total). The subsequent 8 participants will be allocated to the MP cohort and randomly allocated to receive either rozanolixizumab [REDACTED] (6 participants total) or placebo (2 participants total).

The treatment groups are planned to be as follows:

- Cohort 1 (participants with a body weight of  $\geq 35$ kg to  $< 50$ kg) is planned to have 6 participants receive rozanolixizumab [REDACTED] and 2 participants receive placebo via syringe driver at a [REDACTED].
- Cohort 2 (participants with a body weight of  $\geq 35$ kg to  $< 50$ kg) is planned to have 6 participants receive rozanolixizumab [REDACTED] and 2 participants receive placebo via MP through self-administration at a [REDACTED].
- Cohort 3 (participants with a body weight of  $\geq 50$ kg) is planned to have 6 participants receive rozanolixizumab [REDACTED] and 2 participants receive placebo via syringe driver at a [REDACTED].
- Cohort 4 (participants with a body weight of  $\geq 50$ kg) is planned to have 6 participants receive rozanolixizumab [REDACTED] and 2 participants receive placebo via MP through self-administration at a [REDACTED].

Since a [REDACTED] rozanolixizumab fixed dose has not been investigated thus far in lower weight (35 to 50kg) healthy participants, 2 sentinel study participants (1 active + 1 placebo) will be incorporated into Cohort 1 in order to collect safety and tolerability data over a 72-hour period. The SMC will convene to evaluate all available safety and tolerability data following completion of a 72-hour evaluation period and prior to staggered dosing of remaining participants in Cohort 1. As a further precautionary step for Cohort 1, dosing of the 6 post-sentinel participants will be staggered such that no more than 2 participants will be dosed in a 72-hour period with a

minimum of 48 hours between participants. In addition, the Rapid Alert process is in place throughout the study to ensure that exposure to the study medication is stopped if a reported event meets the stopping criteria (see Appendix 8 [Section 10.8]). Cohorts are not obliged to run in numerical sequence (ie, cohorts could run in parallel).

Since MP IMP administrations in this study will likely be at higher infusion rates than the [REDACTED] SC rate undertaken in all rozanolixizumab clinical studies to date, 2 sentinel study participants (1 active + 1 placebo) will be incorporated into Cohorts 2 and 4. Review of 48-hour postdose safety data by the SMC will enable dosing of the remaining participants (see Section 9.7 and Appendix 8 [Section 10.8]).

The eligibility of study participants will be determined during a Screening Period of up to 4 weeks (Day -28 to Day -2). Once eligibility is confirmed, the study participant will be admitted to the site (at Day -1 or the evening of Day -2) and will enter an In-Clinic Period through Day 5. Each study participant will receive a [REDACTED] SC dose of rozanolixizumab on Day 1 and may be discharged beginning at Day 5 at the discretion of the investigator. Each participant will only receive [REDACTED] IMP administration.

Beginning at Day 6, study participants will enter the Ambulatory Period and will attend the clinical site for study visits through Day 57 to allow sufficient time for systemic IgG levels to return to Baseline and for the assessment of anti-drug antibodies (ADAs).

The total maximum study duration per study participant is up to 12 weeks. This includes a 4-week Screening Period, 5-day In-Clinic Period, and the Ambulatory Period from Day 7 through Day 57.

Photographs of the infusion site will be taken, without participant personal or facial identification, for all participants prior to start and 30 minutes after the end of the IMP administration, and additionally upon occurrence of any injection site reaction.

